5.7 Previous and Concomitant Medications

5.7.1 Permitted Concomitant Medications

Any medication the subject takes other than the study drug, including herbal and other non-traditional remedies, is considered a concomitant medication. All concomitant medications must be recorded in the eCRF. The following information must be recorded in the eCRF for each concomitant medication: generic name, route of administration, start date, stop date, dosage, and indication. Any changes in the dosage or regimen of a concomitant medication must be recorded in the eCRF.

At Screening, subjects will be asked what medications they have taken during the last 3 months. At each subsequent study visit, subjects will be asked what concomitant medications they are currently taking.

5.7.2 Prohibited Concomitant Medications

Strong inhibitors of CYP3A4, including protease inhibitors (atazanavir, indinavir, ritonavir, saquinavir, nelfinavir), azole antifungals (ketoconazole, itraconazole, fluconazole), macrolide antibiotics (erythromycin, clarithromycin, telithromycin), calcium channel blockers (verapamil and diltiazem) and grapefruit juice are prohibited during the study.

Strong inducers of CYP3A4, including rifampicin, phenytoin, phenobarbital, carbamazepine, dexamethasone and St. John's Wort (herbal supplement) are prohibited during the study.

Subjects requiring treatment with prohibited concomitant medications should be withdrawn from the study.

6 VARIABLES AND METHODS OF ASSESSMENT

6.1 Efficacy Variables

It is strongly recommended that one rater is assigned for each subject for each of the efficacy assessment scales described below, so that one rater scores a subject's assessment for the entire study. For example, the rater assigned to perform the MMSE would rate that scale for all visits for that subject.

6.1.1 Primary Efficacy Variable

The primary efficacy variable for the study is the ADAS-Cog.

The ADAS-Cog is a brief measure of cognition, including word recall, commands, constructional praxis, naming objects and fingers, ideational praxis, orientation, word recognition, remembering test instructions, spoken language ability, word-finding difficulty, and comprehension of spoken language.

The ADAS-Cog will be administered to the subject and scored by a qualified, trained rater at screening, baseline and at Weeks 4, 13 and 26 as indicated in the Schedule of Procedures ([Table 3](#)).

Further details regarding the assessment are provided in [Appendix 1](#).

6.1.2 Secondary Efficacy Variables

6.1.2.1 Clinical Dementia Rating Scale – Sum of Boxes

The Washington University Clinical Dementia Rating Scale (CDR) is a global assessment of cognition and function rated in 6 domains: memory, orientation, judgment and problem solving, community affairs, home and hobbies, and personal care, which is used to assess the severity of dementia.

Each domain is rated on a 5-point scale of functioning as follows:

- 0: no impairment
- 0.5: questionable impairment
- 1: mild impairment
- 2: moderate impairment
- 3: severe impairment

Personal care is scored on a 4-point scale without a 0.5 rating available.

The CDR will be administered through semi-structured interviews to the subjects and caregivers by a qualified, trained rater at baseline and Weeks 4, 13 and 26 as indicated in the Schedule of Procedures ([Table 3](#)). The CDR-SB score will be obtained by summing each of the domain box scores (i.e., sum of boxes), with scores ranging from 0 to 18.

Further details regarding the assessment are provided in [Appendix 2](#).

6.1.2.2 Mini-Mental State Examination

The MMSE is a brief cognitive screening measure and assesses orientation to time and place, immediate and delayed recall of words, attention and calculation, language (naming, comprehension and repetition), and spatial ability (copying a figure). The

MMSE will be administered to the subject and scored by a qualified, trained rater at screening, baseline and Weeks 4, 13 and 26 as indicated in the Schedule of Procedures (Table 3).

Further details regarding the assessment are provided in Appendix 3.

6.1.2.3 *Alzheimer's Disease Co-operative Study Activity of Daily Living (ADCS-ADL)*

The ADCS-ADL is a validated scale for measuring functional abilities in activities of daily living in subjects with Alzheimer's disease. It measures 6 basic and 17 instrumental activities of daily living and was specifically developed as a sensitive tool to track changes in functional performance in Alzheimer's disease over time. The basic activities include self-care tasks such as eating, walking, toileting, bathing, grooming, and dressing. The instrumental activities are more complex skills that are required to successfully live independently and include shopping, keeping appointments, traveling outside of home, making a meal or snack, reading, and writing. It will be administered to the subject's caregiver and scored by a qualified, trained rater at baseline and Weeks 4, 13 and 26 as indicated in the Schedule of Procedures (Table 3).

Further details regarding the assessment are provided in Appendix 4.

6.1.2.4 *Neuropsychiatric Inventory*

The NPI is an interview-based tool for assessing behavioral domains common in dementia (hallucinations, delusions, agitation/aggression, dysphoria/depression, anxiety, irritability, disinhibition, euphoria, apathy, aberrant motor behavior, sleep and night-time behavior change, appetite and eating change) in terms of frequency, severity and distress. The NPI will be administered to the subject's caregiver and scored by a qualified, trained rater at baseline and Weeks 4, 13 and 26 as indicated in the Schedule of Procedures (Table 3).

Further details regarding the assessment are provided in Appendix 5.

6.1.2.5 *Cornell Scale for Depression and Dementia*

The C-SDD was specifically developed to assess signs and symptoms of major depression in demented subjects.

The scale contains nineteen questions, each of which can be given a score ranging from 0 (absent) to 2 (severe) and is divided into five sub-scales:

- mood-related signs: anxiety, sadness, a minimal reaction to pleasant events and irritability
- behavioral disturbance: agitation, psychomotor retardation, multiple physical complaints and loss of interest
- physical signs: loss of appetite, weight loss and lack of energy
- cyclic functions: diurnal variation in mood, difficulty falling asleep, multiple awakening during the night and early morning awakening
- ideational disturbance: suicidal tendencies, low self-esteem, pessimism and mood-congruent delusions

The C-SDD will be administered through semi-structured interviews to the subjects and caregivers by a qualified trained rater at screening, baseline and Weeks 4, 13, 26 and 30 as indicated in the Schedule of Procedures ([Table 3](#)).

Further details regarding the assessment are provided in [Appendix 6](#).

6.2 Safety Variables

6.2.1 Adverse Events

6.2.1.1 Collection of Adverse Events

It is the responsibility of the Investigator to collect all AEs (both serious and non-serious) derived by spontaneous, unsolicited reports of subjects, by observation and by routine open questionings e.g., "How have you felt since I last saw you?"

6.2.1.2 Definitions

An AE is any untoward medical-occurrence that occurs in a subject or clinical investigation subject administered a pharmaceutical product, and which does not necessarily have to have a causal relationship with this treatment. An AE can therefore be any unfavorable and unintended sign (including abnormal laboratory finding), symptom, or disease temporally associated with the use of an investigational product, whether or not considered related to the product.

All AEs, including intercurrent illnesses, occurring during the study will be documented in the eCRF. Concomitant illnesses, which existed before entry into the study, will not be considered AEs unless they worsen during the treatment period. All AEs, regardless of the source of identification (e.g., physical examination, laboratory assessment, ECG, reported by subject), must be documented.

Pre-existing conditions will be recorded in the eCRF on the Medical History or appropriate page.

A treatment-emergent AE (TEAE) will be defined as an AE that begins or that worsens in severity after at least one dose of study drug has been administered.

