3 OVERALL DESIGN AND PLAN OF THE STUDY

3.1 Overview

This is a phase 2A, proof-of-concept, 26-week, double-blind, multicenter, randomized, parallel group, placebo-controlled study to compare the efficacy and safety of treatment with SUVN-502 (50 mg or 100 mg qd) to placebo treatment in subjects with moderate Alzheimer’s disease receiving donepezil HCl (10 mg qd) and either memantine HCl (10 mg twice daily [bid]) or Namenda XR® (28 mg memantine HCl extended-release qd) or the combination therapy, Namzaric™ (28 mg memantine HCl extended-release / 10 mg donepezil HCl) qd.

The study consists of a 2 to 4-week screening period, followed by a 26-week double-blind treatment period and a 4-week single-blind placebo washout period (Figure 1).

qd: once daily

Figure 1: Study Design

At the screening visit, subjects and their caregiver or appropriate legal representative will sign the informed consent form prior to any procedures. The inclusion and exclusion criteria will be reviewed including demographics, medical history and prior and concomitant treatment, NINCDS-ADRDA criteria, MMSE, Modified Hachinski Ischemic Scale (MHIS), and C-SSRS. If no magnetic resonance imaging (MRI) or computed tomography (CT) scan was performed within the past 12 months, a MRI or CT scan will be performed at screening to confirm that findings are consistent with the diagnosis of dementia due to Alzheimer’s disease without any other clinically significant comorbid pathologies. Subjects will undergo physical and neurological examination, blood pressure assessment, electrocardiogram (ECG). Urine and blood samples will be collected for laboratory evaluations (including pregnancy test for women of childbearing potential) and plasma levels of donepezil and memantine. The ADAS-Cog and C-SDD scores will also be obtained.

The baseline visit will occur 14 to 28 days after screening. Inclusion and exclusion criteria will be reviewed to confirm eligibility of the subject. Subjects will be evaluated

for AEs and undergo physical and neurological examination, blood pressure assessment, and ECG. Urine and blood samples will be collected for laboratory evaluations and APO-E genotype testing. Baseline scores will be assessed for the MMSE, ADAS-Cog, CDR-SB, ADCS-ADL, NPI, C-SDD and C-SSRS.

Following confirmation of eligibility, subjects will be randomized in a 1:1:1 ratio to one of the following three treatment groups:

- SUVN-502 (50 mg)
- SUVN-502 (100 mg)
- Placebo

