Blinded SUVN-502/placebo treatment and generic formulations of donepezil HCl 10 mg and memantine HCl 10 mg will be dispensed to the subjects for treatment until the next visit.

During the 26-week treatment period, subjects and caregivers will have study visits at Weeks 4, 13, and 26. At each of these visits, subjects will be evaluated for AEs and undergo physical and neurological examination, blood pressure assessment, and ECG. The MMSE, ADAS-Cog, CDR-SB, ADCS-ADL, NPI, C-SDD and C-SSRS scores will be assessed. Urine and blood samples for laboratory evaluations will be collected at Weeks 4 (liver function tests only), 13 and 26. For women of childbearing potential, a pregnancy test will be performed at Week 26. Blood samples for plasma levels of SUVN-502, its metabolite (M1 of SUVN-502), donepezil and memantine will be collected at Weeks 4 and 26.

Subjects who complete the 26-week treatment period, will undergo a 4-week single-blind placebo washout period. At Week 30, subjects will attend a follow-up visit to the study center. During this visit, subjects will be evaluated for AEs and undergo physical and neurological examination, blood pressure assessment, ECG, laboratory evaluations. The C-SDD and C-SSRS scores will be assessed.

Subjects who discontinue treatment prematurely (see Section 4.3) should attend a final visit similar to Week 26 visit and, if subjects agree, the subjects will return 4 weeks later for a follow-up visit similar to Week 30 visit.

During the course of the study, an independent Data and Safety Monitoring Board (DSMB) will be assembled to periodically review and evaluate accumulated study data for subject safety, study conduct and progress. The DSMB will have the responsibility to make recommendations concerning continuation, modification, or termination of the study.

The approximate blood volume to be collected during the study is 135.5 mL, with a maximum of 26 mL per visit.

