6.2.1.4 Recording Adverse Events

The period for adverse event reporting will extend from signing of informed consent until 14 days after the last study treatment administration (including placebo during the single-blind placebo washout period). Adverse events occurring after the end of the study should be reported to the Sponsor or Sponsor's designee by the Investigator if the Investigator considers there is a causal relationship with the study drug.

All AEs, regardless of the relationship to study drug, will be recorded in the eCRF. All AE reports should contain a brief description of the event, date and time of onset, date and time of resolution, intensity, treatment required, relationship to study drug, action taken with the study drug, outcome, and whether the event is classified as serious.

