6.2.1.5 Reporting Serious Adverse Events

The Investigator must report any SAEs to the [REDACTED] Clinical Studies Safety Center within 24 hours of becoming aware of the event.

When calling to report an SAE, state that you are reporting an SAE and give the Investigator's name, your name, the telephone number where you can be reached, and the protocol number and title.

The Investigator and the Sponsor (or Sponsor's designee) will review each SAE report and the Sponsor, [REDACTED] will evaluate the seriousness and the causal relationship of the event to study treatment. In addition, the Sponsor (or Sponsor's designee) will evaluate the expectedness according to the reference document (Investigator Brochure or Summary of Product Characteristics). Based on the Investigator and Sponsor's assessment of the event, a decision will be made concerning the need for further action.

All SAEs will be recorded from signing of informed consent until 14 days after the last study treatment administration (including placebo during the single-blind placebo washout period). Serious AEs occurring after the end of the study and coming to the attention of the Investigator must be reported only if they are considered (in the opinion of the Investigator) causally-related to the investigational drug.

- [REDACTED]
1. Telephone the Medical Monitor to inform her that you are faxing a SAE form. If the Medical Monitor is not available or you are calling after business hours (8:30 am to 5:30 pm Eastern time, Monday to Friday), leave a message in her voice mailbox.
 2. Provide the Medical Monitor with the Principal Investigator's name, your name, the telephone number where you can be reached, and the protocol number and title.
 3. Fax the SAE form and any supporting documentation to the Medical Monitor within 24 hours of becoming aware of the event.
 4. After business hours, the Medical Monitor may be reached through [REDACTED] 24-hour answering service [REDACTED]. Give the answering service the protocol number, the study drug name, and the Sponsoring pharmaceutical company.

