7.2.5 Week 26 Visit (Visit 5, Day 182)

The following procedures will be performed at Week 26 (Day 182±3 days) of the study:

- AE review
- Concomitant medications review
- Plasma sample for measurement of SUVN-502, M1 of SUVN-502, donepezil and memantine levels
- Study drug compliance check and dispensation
- Blood and urine samples for clinical laboratory tests, including pregnancy test for women of childbearing potential
- Physical and neurological examinations
- Blood pressure measurement
- MMSE
- ADAS-Cog
- CDR-SB, ADCS-ADL, NPI and C-SDD
- C-SSRS (since last visit version)
- ECG 3 hours post-treatment

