4.8.1 Extent of Exposure

Exposure as measured by duration of treatment will be summarized by treatment group. Extent of exposure will be calculated for the Treatment Period (up to Week 26).

Days of exposure will be calculated for each subject: (date of last dose of treatment drug – date of first dose + 1).

The duration of study participation including the follow-up period will also be summarized by treatment group.

The duration of study participation will be calculated as (the latest of (last visit/follow-up date or study termination date) – randomization date + 1. For subjects who die during the study, time of study will be calculated as (date of death – randomization date) + 1.

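### Protocol 6.2.1.2 counts worsening of a pre-existing illness as an AE only in the treatment period, which conflicts with the AE/SAE recording window and the TEAE definition

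*Protocol*

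**What the plan says.** Four rules in the protocol bear on the same event.

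- **Status of pre-existing illness** (6.2.1.2): "Concomitant illnesses, which existed before entry into the study, will not be considered AEs unless they worsen during the treatment period".
- **Recording window for AEs** (6.2.1.4): "The period for adverse event reporting will extend from signing of informed consent until 14 days after the last study treatment administration". The sentence goes on to include placebo taken in the washout.
- **Recording window for SAEs** (6.2.1.5): "All SAEs will be recorded from signing of informed consent until 14 days after the last study treatment administration", with the same inclusion of washout placebo.
- **TEAE definition** (6.2.1.2, same section as the first rule): "an AE that begins or that worsens in severity after at least one dose of study drug has been administered". SAP 4.8.2 repeats it in substance, also without an end date.

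The study periods are set in protocol 3.1: a screening period, "followed by a 26-week double-blind treatment period and a 4-week single-blind placebo washout period". The same section adds: "Subjects who complete the 26-week treatment period, will undergo a 4-week single-blind placebo washout period".

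**The concern.** The first rule is narrower than the other three. AEs are still being collected after Week 26, but for one class of event the definition of an AE appears to have closed. The TEAE definition cannot repair this, because it operates only on something already recorded as an AE.

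The class matters in this trial. Protocol 4.2 admits subjects with treated and controlled prior major depression, with stable low-dose antipsychotics for sleep disturbance, agitation or aggression, and with controlled hypertension. Protocol 1.1.3 gives a mean half-life of 12.5 to 13.7 hours, so SUVN-502 clears early in the washout. If stopping it has an effect, that effect could plausibly appear as worsening of a condition already on the medical history page. Such an event would be dropped, while a new-onset event on the same day would be kept. Sites that interpret the period differently would also record differently.

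**Working it through.** The plan gives no figure on this point to reproduce. The check compares the texts and lays out the nominal timeline.

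**1. What the treatment period means.** Protocol 3.1 places the washout after it. Table 3 (7.1) puts end of treatment at Week 26 and labels Week 30 as follow-up. Protocol 9.10 counts 26 weeks of treatment and 4 weeks of follow-up separately. SAP 4.8.1 describes the period as running to Week 26. The usage is consistent, although 6.2.1.2 does not itself define the term.

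**2. Post-treatment gap for a completer.**
- End of treatment period: Day 182 (7.2.5).
- End of washout: Day 210 (7.2.6).
- End of recording: 210 + 14 = Day 224.
- Gap: (210 − 182) + 14 = 28 + 14 = 42 days.
- Share of days from first dose: 42/224 = 18.75%.

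The visit windows (±3 days at Week 26, ±2 at Week 30) move this only a little:
- Shortest gap: (208 − 185) + 14 = 37 days, and 37/222 = 16.7%.
- Longest gap: (212 − 179) + 14 = 47 days, and 47/226 = 20.8%.

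**3. Screening.** Recording starts at consent, 14 to 28 days before baseline, so worsening before the first dose is outside the treatment period too. With 28 screening days the share is (28 + 42)/(28 + 224) = 70/252 = 27.8%. These days say nothing about withdrawal effects, and SAP 4.8.2 only lists pre-treatment events. The 42-day figure is therefore the relevant one.

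**4. What is kept in the gap.**
- New-onset events: 6.2.1.2 limits only pre-existing illness.
- Laboratory results judged significantly worse than baseline: 6.2.2 makes these AEs with no period limit.
- Suicidal ideation or behavior: 6.2.6.1 makes every report an AE.

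Worsening agitation, depression without suicidality, hypertension or cardiac disease has no such rule. At Week 30 the C-SDD, blood pressure and ECG are scheduled; the NPI is not (Table 3).

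**5. Serious worsening.** Protocol 6.2.1.3.1 defines an SAE by an untoward occurrence plus a seriousness criterion such as inpatient hospitalization. It has no exclusion for pre-existing illness and no period limit, and 6.2.1.5 requires SAEs to be recorded through washout plus 14 days. A Week 28 hospitalization for worsened pre-existing disease meets that definition. But 6.2.1.1 presents serious and non-serious as two kinds of AE, and 6.2.1.3 assesses seriousness for each AE. A reader working in that order could stop at 6.2.1.2.

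**6. Illustrative count.** The documents give no rate, so 2-10% is an assumption.
- Randomized to SUVN-502: 2 × 179 = 358.
- Completers at the 20% drop-out allowed in 8.9: 358 × 0.80 ≈ 286.
- 286 × 0.02 ≈ 6; 286 × 0.10 ≈ 29.

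**The case against.** The strongest case against the point is that 6.2.1, read as a whole, already covers these events. The recording rules count washout placebo as study treatment, and 5.1.1 lists it under investigational treatment, so an investigator has some basis for reading the treatment period broadly. Protocol 6.2.1.2 also asks for all AEs during the study to be documented. Week 30 includes an AE review, examinations, laboratory tests, blood pressure, ECG, C-SDD and C-SSRS, and those data are kept whether or not an AE form is completed. Under 6.2.5 the investigator judges whether a post-treatment physical or neurological abnormality is an AE. The rule applies to all arms alike, and the SAP plans no separate washout AE table that it could distort.

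Part of this stands. The loss is not certain, because some sites will record the events anyway, and several conditions are measured at Week 30. It does not remove the conflict. The broad reading goes against the way both documents use the term, and documenting all AEs does not help if the event is defined as not being one. A single Week 30 measurement is also not a record of onset, severity, causality and outcome.

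A reader might go further and infer that a hospitalization in washout for worsened pre-existing illness is neither an AE nor an SAE and triggers no 24-hour report. The documents do not support that: the SAE definition stands on its own and the SAE window runs through washout. Sections 6.2.1.1 and 6.2.1.3 make the text ambiguous, no more. It would likewise be conjecture to say that withdrawal effects would mostly take the form of worsened pre-existing conditions.

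**Conclusion.** The point holds as a definitional conflict with a practical consequence. Taken literally, 6.2.1.2 removes non-serious worsening of pre-existing illness from the AE record for 42 of 224 nominal days after first dose (18.75%) in a completer, and also before the first dose, while new-onset events are recorded throughout. Laboratory worsening and suicidality are outside the gap. For serious worsening the correct statement is that it is reportable but that the text should say so plainly.

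The day counts rest on nominal visits and on the 26-week meaning of the treatment period. The figure of 6 to 29 subjects rests on an assumed 2-10% rate and on 20% drop-out. A reader might apply that rate to all 358 randomized SUVN-502 subjects, but those who terminate early do not enter the placebo washout (7.2.7 asks only for a follow-up visit). No sample size, power or error rate is affected. The change is worth making because it is small and the omission is selective.

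**What to change.** In protocol 6.2.1.2, replace the final condition of the sentence on concomitant illnesses with: *unless they worsen at any time during the AE recording period defined in 6.2.1.4*. This aligns it with 6.2.1.4, 6.2.1.5 and the TEAE definition.

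Then reconcile 6.2.1.2, 6.2.1.3, 6.2.1.3.1, 6.2.1.4 and 6.2.1.5 by adding one sentence: worsening of a pre-existing illness in that period which meets a seriousness criterion is an SAE and is reported under 6.2.1.5. Repeat both statements in the eCRF completion guideline so that sites record alike.

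The cost is one changed phrase, one added sentence, a guideline note and a few more AE records. No visit or procedure is added, and the TEAE rule in SAP 4.8.2 needs no change.
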